### 2.2.4. Stopping Rules for mCRM Algorithm

[figure not shown]
The mCRM process will be continued until at least one of the following stopping rules is met:

1. *Maximum sample size of 51 subjects has been reached.*

2. *MTD has been identified with sufficient accuracy, ie, 12 subjects have been accumulated on a dose that is currently estimated to be the MTD.*
3. *All doses appear to be overly toxic and MTD cannot be determined in the current trial setting.*

The following (Figure 1) is a schematic of the mCRM design incorporating the sequential dosing decision process.

**Figure 1. mCRM Design Schematic**

### **3. ENDPOINTS AND BASELINE VARIABLES: DEFINITIONS AND CONVENTIONS**

#### **3.1. Primary Endpoint(s)**

Primary endpoints of the study include the following safety endpoints.

##### **3.1.1. Treatment emergent TIEs through Day 8**

Thromboembolic and/or ischemic events (TIEs) are defined as any of the listed events at the respective severity grade indicated in Appendix 1. The first primary endpoint is defined as

the frequency of treatment emergent TIEs in subjects treated with PF-05230907 through Day 8. For the respective event to count as a treatment emergent TIE, onset or worsening of the event must occur following treatment with PF-05230907 and during the interval between Day 1 dosing through Day 8.

### **3.1.2. Treatment emergent Adverse Events**

Severity of adverse events (AEs) and serious adverse events (SAEs) will be graded according to the National Cancer Institute (NCI) Common Terminology Criteria for Adverse Events (CTCAE) version 4.03. Any events occurring following the start of treatment or increasing in severity will be counted as treatment emergent. The second and third primary endpoints are defined as follows:

- Treatment emergent AEs as characterized by type, frequency, severity, timing, seriousness and relationship to study treatment through Day 8.
- Treatment emergent SAEs as characterized by type, frequency, severity, timing, seriousness and relationship to study treatment through Day 43.

### **3.1.3. Treatment emergent laboratory abnormalities**

The fourth primary endpoint is defined as treatment emergent laboratory abnormalities as characterized by type, frequency, and severity through Day 4 (Day 8/discharge for D-dimer).

The clinical laboratory safety parameters in this evaluation include hematology, blood chemistry, Prothrombin Time/International Normalized Ratio (PT/INR), fibrinogen, ATIII, Protein S level, Protein C activity, cardiac troponin I (local or central laboratory), D-dimer (local laboratory), and urinalysis. All test measurements are obtained from the central laboratory unless otherwise noted in the protocol. Any abnormalities occurring after the administration of treatment and increasing in severity from baseline value will be counted as treatment emergent.

### **3.1.4. Physical Examination Changes**

The fifth primary endpoint is defined as physical examination changes through Day 8 or discharge, whichever is earlier. Comprehensive physical examination consists of assessments of general appearance, HEENT, skin, heart (auscultation), lungs (auscultation), abdomen (palpitation and auscultation), and extremities with attention to swelling, general or localized tenderness, entire leg or calf swelling, edema, and collateral superficial veins. The comprehensive physical examination is scheduled at screening (baseline) and Day 8 (or discharge).

A targeted physical examination will include the following parameters and body systems: general appearance, skin, heart (auscultation), lungs (auscultation), abdomen (palpitation and auscultation), and extremities with attention to swelling, general or

localized tenderness, entire leg or calf swelling, edema, and collateral superficial veins. The targeted physical examination is scheduled at Day 2, Day 3, and Day 4.

The results of the comprehensive and targeted physical examinations will be combined to evaluate the changes from baseline through Day 8 (or discharge) for each parameter.

### **3.1.5. Vital Signs Changes**

The sixth primary endpoint is defined as vital signs changes through Day 8 (or discharge). Blood pressure, pulse rate, respiratory rate (supine) and temperature will be measured at multiple times specified in Schedule of Activities (SoA) of the Protocol.

### **3.1.6. Electrocardiogram (ECG) Results**

The seventh primary endpoint includes the ECG results through Day 8 (or discharge). A single standard supine 12-lead ECG should be performed after the subject has rested quietly for at least 10 minutes in a supine position at Day 1, Day 2, Day 4, and Day 8 (or discharge). The Day 1 screening ECG values will serve as each subject's baseline values. If a scheduled single ECG assessment reveals a clinically significant abnormality (other than the Day 1 screening value) then 2 additional ECGs should be collected to confirm the original observation. Clinically significant abnormalities that represent a change from the Day 1 screening/baseline visit can be recorded as AEs.

## **3.2. Secondary Endpoint(s)**

### **3.2.1. Pharmacodynamic Endpoint**

The pharmacodynamic endpoint includes changes in activated partial thromboplastin time (aPTT) and plasma prothrombin fragments 1+2 (PF1+2), after dosing with study drug through Day 2.

### **3.2.2. Immunogenicity Endpoint**

The immunogenicity endpoint includes anti-drug antibody (ADA), neutralizing anti-PF-05230907 antibody (NAb), and Factor X activity through Day 43 and/or Day 91 follow-up visit. Blood samples for this endpoint will be collected at the time points described in SoA and analyzed.

## **3.3. Exploratory Endpoints**

### **3.3.1. Hemostatic Endpoint**

*ICH absolute and CCI* [REDACTED] *from baseline volume at 24 hours are exploratory endpoints. A diagnostic brain CT scan completed within 6.0 hours from subject's spontaneous intracerebral hemorrhage symptom onset will provide a baseline ICH volume*

assessed by the ABC/2 method for purposes of determining study eligibility. The CT scan completed at baseline and at 24 hours will be sent to the central vendor for final analysis. The ICH volume obtained from the central vendor will be used to assess the ICH absolute and **CCI** [REDACTED] from baseline.

Another exploratory endpoint includes *CT parameters that may inform future investigations of PF-05230907 and/or the condition of ICH.*

### **3.3.2. Neurological Outcome**

*Neurologic function as assessed by the National Institutes of Health Stroke Scale (NIHSS)* is an exploratory endpoint. *The NIHSS is a 15-item neurologic examination stroke scale used to evaluate the effect of acute cerebral infarction on the levels of consciousness, language, neglect, visual-field loss, extraocular movement, motor strength, ataxia, dysarthria, and sensory loss.* The NIHSS will be conducted at Screening, Day 1, Day 2, Day 4, Day 43, and Day 91.

### **3.3.3. Pharmacokinetics**

*PF-05230907 concentration in plasma* is an exploratory endpoint. Blood samples will be collected at screening, 5 minutes and 45 minutes post-dose for this evaluation. *Samples obtained within 10% of the nominal time (eg, within 6 minutes of a 60 minute sample) from dosing or  $\pm 2$  minute for samples less than 10 minutes from dosing will not be captured as a protocol deviation.*

### **3.3.4. Exploratory Biomarkers**

*Some of the planned biomarker(s) may not be performed if not supported by data from the ongoing pre-clinical work.*

#### **3.3.4.1. Pharmacodynamic Biomarkers**

*Change in other exploratory biomarkers that may reflect pharmacologic effect of PF-05230907 or ICH progression may be evaluated.*

#### **3.3.4.2. Neuro-inflammation Biomarkers**

Exploratory endpoint includes *potential biomarkers of neuro-inflammation and/or neurological outcomes to better understand ICH and/or its outcomes.*

### **3.3.5. Immunogenicity**

*Anti-Chinese hamster ovary (CHO) protein antibodies and anti-paired basic amino acid cleaving enzyme (PACE) furin antibodies* are exploratory endpoints. Blood samples will be collected at screening and Day 43 for this evaluation.

### **3.3.6. Health Resource utilization**

*Surrogate measures for health resource utilization, may include duration of stay in stroke/ICU unit, duration of hospital stay, duration of inpatient rehabilitation, and duration of outpatient rehabilitation.*

## **3.4. Baseline Variables**

### **3.4.1. Baseline Definitions**

In this study, “study drug” refers to PF-05230907, “dose group” refers to the group of subjects dosed at the same dose level. Measurements or endpoints will be collected or derived at all visits as specified in the SoA of the protocol. The visits must be performed within the pre-specified visit window as stated in the protocol.

The last available assessment prior to the administration of study drug at Day 1 is defined as “baseline” value or assessment for all analyses unless specifically stated otherwise. If assessment dates are collected, the observed date will be used to determine pre-dose time point from the date of study drug administration for baseline calculation. Otherwise, if an assessment is planned to be performed prior to the administration of study drug in the protocol and the assessment is performed on the same day as the administration of study drug, it will be assumed that it was performed prior to study treatment administration for assessment that the time is not collected or missing.

Analyses involving baseline covariates will only include covariates measured at or before study treatment.

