Abbreviations: → = ongoing/continuous event; ADA = anti-drug antibody; AEs = adverse events; Anti-CHO = anti-Chinese hamster ovary; anti-PACE = anti-paired basic amino acid cleaving enzyme; aPTT = activated partial thromboplastin time; ATIII = antithrombin III; BP = blood pressure; CT = computed tomography; ECG = electrocardiogram; FX = factor X; Hr = hour(s); HRU = health resource utilization; ICU = intensive care unit; IVH = intraventricular hemorrhage; Min = minute(s); MR = magnetic resonance; mRS = modified rankin scale; NAb = neutralizing antibody; PD = pharmacodynamic; PF1+2 = prothrombin fragment 1+2; PK = pharmacokinetic; PT/INR = prothrombin time/international normalized ratio; PTT = partial thromboplastin time; SAEs = serious adverse events; TFPI = tissue factor pathway inhibitor.

a. Subjects in the study must stay in the hospital/stroke unit/ICU at a minimum through Day 4. If a subject is discharged on Day 4 see [Section 6.2.8](#).

- b. See [Section 6.2.9](#) if subject was discharged prior to Day 8.
- c. Day relative to start of study treatment (Day 1).
- d. ICH related information from medical records (such as Glasgow Coma Scale [GCS] assessment by emergency medical services, CT scan and ICH characteristics, vital signs, ECG, physical examination, laboratory test results, demography, weight, medical history, concomitant medications, concomitant treatments) which is collected prior to the time of consent but within 6.0 hours of ICH symptom onset may be used to assist with inclusion/exclusion determination.
- e. If the following cannot be collected during the Screening Day 1 period, the site may collect as soon as possible post-dose but prior to Day 4-see [Section 6.1](#):
 - Demography that does not affect eligibility (race and ethnicity).
 - Prothrombin G20210A Mutation.
 - Factor V Leiden Mutation.
 - Urinalysis (if not collected pre-dose collect as soon as possible post-dose).
 - Prep D1 banked biospecimen (unless prohibited by local regulations or ethics committee decision) and additional consent to allow banked biospecimen Prep D1 to be used for additional purposes (unless prohibited by local regulations or ethics committee decision).
 - Medical history that does not affect eligibility.

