- Obtain lower extremity Doppler Ultrasonography. If lower extremity Doppler Ultrasonography cannot be collected during the Screening Day 1 period, the site may collect this data as soon as possible post-dose; no nicotine intake should occur for approximately 1 hour prior to testing.
- Monitoring of serious adverse events.
- Review inclusion/exclusion criteria. Ensure subject meets screening entry criteria.
- Treatment allocation after eligibility is confirmed.

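### SAP 3.4.1 assumes untimed dosing-day assessments are pre-dose, but the protocol lets the screening Doppler, NIHSS and urinalysis be done after dosing, so a post-dose result can be labelled baseline

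*SAP*

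**What the plan says.** SAP 3.4.1 defines baseline as the last assessment before study drug and applies this "for all analyses unless specifically stated otherwise". It then gives a default for same-day assessments with no time available: "if an assessment is planned to be performed prior to the administration of study drug in the protocol", and it was done on the dosing date, "it will be assumed that it was performed prior to study treatment administration".

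The protocol plans the lower-extremity Doppler, NIHSS and urinalysis at Screening. Footnote e of the Schedule of Activities says that if the listed items cannot be obtained then, "the site may collect as soon as possible post-dose but prior to Day 4". All three are on that list. Protocol 6.1 repeats the allowance for the Doppler ("the site may collect this data as soon as possible post-dose"), there without the Day 4 limit, and for urinalysis. For the NIHSS, 6.1 and footnote q ask for an assessment within 2 hours before planned dosing, so only footnote e opens the post-dose route.

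SAP 6.6.6.2 promises a list and summary of treatment-emergent abnormal Doppler results. SAP 3.1.3 includes urinalysis among the laboratory parameters judged against baseline. For a TIE to be treatment emergent, SAP 3.1.1 requires that "onset or worsening of the event must occur following treatment with PF-05230907".

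**The concern.** The SAP default is reasonable when an item planned before dosing can only be done before dosing. For the footnote e items that premise fails, because the protocol itself provides for late collection. Being planned at Screening is then no evidence that the item was done before the bolus.

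The error runs one way. The default can move a post-dose finding to baseline, but it cannot move a pre-dose finding the other way. In a trial whose main risk is thrombosis, a DVT seen on a scan taken hours after dosing could be shown as present at baseline, in an output meant to show new abnormalities.

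**Working it through.** The point is a conflict between passages, so the main check is to follow one subject through the rules.

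1. **Subject.** Dosed on Day 1. The screening Doppler is done later the same day, as footnote e permits. The date is recorded and the time is not. The scan shows a DVT.
2. **SAP 3.4.1.** The item is planned pre-dose, it was done on the dosing date, and its time is missing. All conditions are met, so the scan is labelled baseline.
3. **SAP 6.6.6.2.** For brain imaging this section explains new onset as absent at baseline and present at 72 hours. If treatment emergent is read the same way for the Doppler, which the SAP does not spell out, a DVT on the baseline scan and again on Day 4 is no change. It is left out of the summary.
4. **NIHSS and urinalysis.** By the same steps, a post-dose value becomes the baseline value.

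**Where the rule does not reach**

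- A Doppler with a recorded post-dose time. The default does not apply, and the extended screening window in SAP Table 4 ends at 0 hr.
- A Doppler dated Day 2 or Day 3. It is not on the dosing date, so the subject has no baseline scan. The SAP does not say how emergence is then judged.

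The SAP can write an exception where it wants one: section 6.5.3 says which weight to use when none was measured before dosing. There is no counterpart for the footnote e items.

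**What one lost TIE would do.** This sizes the stronger reading discussed below. It does not show that the rule loses an event. Inputs are Table 3, the Unif[0,3] prior on β, the 15% target, cohorts of 3 and the cap of 2 increments.

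- Reproducing the plan's figure: x = atanh(2p − 1). At 5 µg/kg, p = 0.08 gives atanh(−0.84) = −1.22, as printed. All 15 adjusted doses in Table 3 reproduce to rounding.
- Model: rate at a dose = p^β, with p the Table 3 rate. The posterior of β is proportional to the binomial likelihood on 0 to 3, and its mean was found by numerical integration. The model output is the highest grid dose with rate at or below 15%.
- Example, 1/3 at 5 µg/kg: mean β is 0.72. The rate at 5 is 0.08^0.72 ≈ 0.16, above target; at 4 it is 0.06^0.72 ≈ 0.13, so the output is 4.
- Example, 0/3 at 5 µg/kg: mean β is 1.82. The rate at 19 is 0.325^1.82 ≈ 0.13 and at 24 it is 0.38^1.82 ≈ 0.17, so the output is 19, capped at 8.

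| Cohort | Earlier data | Output with 1/3 | Output with 0/3 |
|---|---|---|---|
| 1 (5 µg/kg) | none | 4 (β 0.72) | 19, capped at 8 (β 1.82) |
| 2 (8 µg/kg) | 0/3 at 5 | 10 (β 1.13) | 24, capped at 12 (β 1.97) |
| 3 (12 µg/kg) | 0/3 at 5 and at 8 | 15 (β 1.52) | 24, capped at 19 (β 2.11) |

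These are model outputs only, before clinical and data monitoring committee review.

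**The case against.** A reader might infer that a DVT mislabelled as baseline drops out of the TIE count and so raises the MTD. The documents do not support that. SAP 3.1.1 turns on onset or worsening of the event after dosing and does not mention a baseline Doppler. TIEs reach the model as site-reported adverse events (Protocol 7.1.8), adverse events are recorded from dosing onward (Protocol 8.2), and the sponsor and investigator document TIEs at Day 8 (footnote m). Partial adverse event dates follow a separate sponsor algorithm (SAP 5.4.4.1), not SAP 3.4.1. The table above therefore shows that any lost TIE would matter, not that this rule loses one. The contrast is also largest in cohort 1; on the 5–8–12 path it falls to one grid step after the cap.

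An indirect route remains. A DVT found only on imaging has no observed onset, so someone judging emergence would naturally look at the baseline scan. That is an inference, not a stated rule.

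Two further objections stand. The default applies only when the time is missing or not collected, and neither document says whether the case report form records a time for these items. The current SAP was also amended after the decision to terminate at 21 enrolled subjects, so a change now affects the final outputs and not past dose assignments.

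A Day 2 or Day 3 scan does not support a claim of under-counting either. With no baseline and a post-dose adverse event record, the error could run toward counting too many.

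**Conclusion.** The conflict is real and narrow. As written, SAP 3.4.1 can label a post-dose Doppler, NIHSS or urinalysis as baseline. The clearest consequence is a DVT missing from the treatment-emergent Doppler summary. The conclusion assumes that treatment emergent in SAP 6.6.6.2 means absent at baseline. It takes effect only if at least one such item was done after dosing on Day 1 with no recorded time. The documents give no frequency, so the number affected runs from none upward.

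No effect on the TIE count or the MTD is shown. At most, a mislabelled baseline could influence a judgement that a DVT was already present. The point merits correction because the rule is explicit, its error runs one way and the repair is almost free.

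**What to change.** Add an exception to SAP 3.4.1. The Doppler, NIHSS and urinalysis listed in footnote e count as baseline only when a recorded date and time confirm collection before dosing. Otherwise they are treated as post-dose and baseline is missing.

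Leave the TIE definition unchanged: onset or worsening after dosing, at the Appendix 1 grade. A rule counting every DVT without a pre-dose scan as a TIE would override both parts of that definition and should not be adopted. If a TIE-grade DVT has no confirmed pre-dose Doppler, report the final MTD estimate with it counted and with it not counted, as a sensitivity analysis.

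The cost is one added SAP rule and, only if such a DVT occurs, one extra model run. Some subjects will have no baseline for these items, and a few findings that were already present may appear as treatment emergent. Flagging them in the listing as lacking a confirmed baseline would make that visible.

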### **3.4.2. Baseline Characteristics**

Baseline characteristics include demographics, physical measurements, body mass index, medical history and smoking history. These baseline characteristics are not planned to be included as stratification variables or covariates in statistical models unless otherwise specified in Section 6.

## **4. ANALYSIS SETS**

Data for all subjects will be assessed to determine if the subjects meet the criteria for inclusion in each analysis population prior to releasing the database.

### **4.1. Full Analysis Set**

The Full Analysis Set (FAS) is defined as all enrolled subjects who receive the study drug PF-05230907. Analyses will be performed on the FAS population unless otherwise specified.

## **4.2. Safety Analysis Set**

The safety analysis set is the same as the FAS. All subjects who receive the study drug will be included in the safety analyses and listings. Subjects will be grouped according to the dose level received at study enrollment.

### **4.2.1. TIE-evaluable Set**

The TIE-evaluable set includes all subjects who receive PF-05230907. All subjects in the TIE-evaluable set will contribute to the determination of the MTD including subjects who are lost to follow-up prior to completion of the TIE observation period from study enrollment through 7 days post-dose (Day 8). For subject(s) meeting protocol deviations (see Section 4.4) that render the subject non-evaluable for the TIE assessment and necessitating a replacement, the replacement subject will be used instead in sensitivity analyses, and mCRM analyses during the trial when deemed appropriate.

## **4.3. Other Analysis Sets**

For other endpoints including PK, PD, brain imaging, immunogenicity, biomarkers analysis sets are defined as all subjects treated with PF-05230907 who have at least one measurement of the corresponding endpoint or measure of interest.

### **4.3.1. Pharmacokinetic Analysis Set**

#### **4.3.1.1. Concentration Analysis Set**

The PK concentration analysis set is defined as all enrolled subjects treated with PF-05230907 who have at least one measurement of PF-05230907 concentration.

#### **4.3.1.2. Parameter Analysis Set**

Noncompartmental parameters will not be calculated for the study report due to the short half life ( $t_{1/2}$ ) and limited sampling.

### **4.3.2. Pharmacodynamic Analysis Set**

The PD analysis set is defined as all enrolled subjects treated with PF-05230907 who have at least one measurement of PD parameters of interest.

### **4.3.3. Immunogenicity Analysis Set**

The immunogenicity analysis population is defined as all enrolled subjects treated who have at least one measurement of post-treatment immunogenicity parameters of interest.

#### **4.4. Protocol Deviations**

A full list of protocol deviations will be compiled and reviewed by clinician, clinical pharmacologist, and statistician to identify major and minor deviations prior to database release. Different protocol deviations may have impact on different analysis populations. At the discretion of the clinician, clinical pharmacologist, and statistician, major violators might be excluded from impacted analysis populations. The decision and rationale for exclusion will be documented. According to the protocol, any deviations from the PK/PD, immunogenicity processing steps, including any actions taken, must be documented and reported to the sponsor. *On a case-by-case basis, the sponsor may make a determination as to whether sample integrity has been compromised. Any sample deemed outside of established stability, or of questionable integrity, will be considered a protocol deviation.*

If dosing error is greater than 20%, then the subject may be excluded from the group statistics of the PK and/or PD analysis when deemed appropriate.

